6.2.2 Specimen Preparation, Handling, and Storage

Urine and breast milk will be aliquoted into bisphenol- and phthalate-free 2 mL tubes (Thermo Scientific, Waltham, MA) within two hours of collection and will be stored at -80°C. Urine and breast milk collection containers/devices will be tested for the presence of phthalates and bisphenols.

CONFIDENTIAL

6.2.3 Specimen Shipment

N/A

6.2.4 Laboratory Evaluations

Chemical analyses. Phthalate metabolites and bisphenols will be analyzed at the NYU Human and Environmental Exposure Assessment Facility Core lab under the supervision of [name].

Bisphenols. Eight bisphenols (BPA, BPAF, BPAP, BPB, BPF, BPP, BPS, and BPZ) will be determined by HPLC-ESI-MS/MS. Concentrations of individual bisphenols will be adjusted for creatinine (Cr) as described below. We will also sum molar concentrations of all individual bisphenols for a total bisphenol concentration.

Phthalate metabolites. Quantitative detection of 22 phthalate metabolites will also involve HPLC-ESI-MS/MS.²² Urine samples will be processed using enzymatic deconjugation of glucuronidated phthalate monoesters, followed by solid phase extraction coupled with reverse-phase HPLC-ESI-MS/MS. Individual phthalate metabolite concentrations will be adjusted for Cr as described below. We will also sum metabolites of parent compounds di-2-ethylhexyl phthalate (DEHP), as well as di-isononyl phthalate (DINP) and di-*n*-octyl phthalate (DNOP), as DINP, DNOP, and di-isodecyl phthalate (DIDP, represented by its metabolite mono-carboxyl isononyl phthalate [mCINP]) are increasingly replacing DEHP in response to consumer advocacy and legislative activity.²³

Creatinine. To account for urinary dilution, urinary Cr will be analyzed using HPLC-ESI-MS/MS as described elsewhere²⁴ and chemical concentrations will be adjusted for Cr via a transformation described by Kuiper et al.,²⁵ with an alternate adjustment method by O'Brien et al.²⁶ and no adjustment explored in sensitivity analyses.

6.3 Study Schedule

6.3.1 Screening

- Diaper Study personnel will identify potential participants from the NYU CHES study database.
- Remote or in-person screening will take place. Refer to Section 4.4 for details.

6.3.2 Enrollment/Baseline

- Diaper Study team member will obtain consent.
- Diaper Study team member will assign participant to study group in alternating fashion. Participants will not be told of their group assignment in advance of delivery or postpartum consent.
- Diaper Study team member will obtain participant's delivery date from participant's EMR and schedule diaper delivery to their home to begin directly afterward or schedule diaper delivery to begin immediately if consent occurs postpartum.

CONFIDENTIAL

6.3.3 Phone Call - 2 Weeks After Delivery

- Diaper Study team member will confirm consent.
- Participants will complete questionnaire by phone.

6.3.4 Phone Call - 6 Weeks After Delivery

- Diaper Study team member will confirm consent.
- Participants will complete questionnaire by phone.

6.3.5 Study Visit

- After using products in assigned study group for up to three months, a single study visit will occur after a routine well-visit or at participant's home between 2 and 3 months after diaper intervention has begun. If visit cannot occur after infant's well-visit, Diaper Study team member will go to participant's home.
- Diaper Study team member will confirm consent.
- Participants will be asked to provide maternal breast milk and urine samples.
- Diaper Study team member will collect infant urine sample.
- Participants will complete questionnaire.

6.3.6 Withdrawal Visit

- No procedures or evaluations will be done and no biospecimens will be collected if a participant withdraws or is terminated early.

6.3.7 Unscheduled Visit

- We do not anticipate unscheduled visits.

7 Safety and Adverse Events

7.1 Definition of Adverse Events (AE)

An **adverse event** (AE) is any symptom, sign, illness or experience that develops or worsens in severity during the course of the study. Intercurrent illnesses or injuries should be regarded as adverse events. Abnormal results of diagnostic procedures are considered to be adverse events if the abnormality:

- results in study withdrawal
- is associated with a serious adverse event

CONFIDENTIAL

- is associated with clinical signs or symptoms
- leads to additional treatment or to further diagnostic tests
- is considered by the investigator to be of clinical significance

7.1.1 Definition of Serious Adverse Events (SAE)

Serious Adverse Event

Adverse events are classified as serious or non-serious. A **serious adverse event** is any AE that is:

- fatal
- life-threatening
- requires or prolongs hospital stay
- results in persistent or significant disability or incapacity
- a congenital anomaly or birth defect
- an important medical event

Important medical events are those that may not be immediately life threatening, but are clearly of major clinical significance. They may jeopardize the subject, and may require intervention to prevent one of the other serious outcomes noted above. For example, drug overdose or abuse, a seizure that did not result in in-patient hospitalization, or intensive treatment of bronchospasm in an emergency department would typically be considered serious.

All adverse events that do not meet any of the criteria for serious should be regarded as **non-serious adverse events**.

7.1.2 Definition of Unanticipated Problems (UP)

Unanticipated Problems Involving Risk to Subjects or Others

Any incident, experience, or outcome that meets all of the following criteria:

- Unexpected in nature, severity, or frequency (i.e. not described in study-related documents such as the IRB-approved protocol or consent form, the investigators brochure, etc.)
- Related or possibly related to participation in the research (i.e. possibly related means there is a reasonable possibility that the incident experience, or outcome may have been caused by the procedures involved in the research)
- Suggests that the research places subjects or others at greater risk of harm (including physical, psychological, economic, or social harm).

7.2 Classification of an Adverse Event

7.2.1 Severity of Event

For AEs not included in the protocol defined grading system, the following guidelines will be used to describe severity.

- **Mild** – Events require minimal or no treatment and do not interfere with the participant's daily activities.

CONFIDENTIAL

- **Moderate** – Events result in a low level of inconvenience or concern with the therapeutic measures. Moderate events may cause some interference with functioning.
- **Severe** – Events interrupt a participant's usual daily activity and may require systemic drug therapy or other treatment. Severe events are usually potentially life-threatening or incapacitating.

7.2.2 Relationship to Study Intervention

The clinician's assessment of an AE's relationship to study intervention is part of the documentation process, but it is not a factor in determining what is or is not reported in the study. If there is any doubt as to whether a clinical observation is an AE, the event should be reported. All AEs must have their relationship to study intervention assessed. In a clinical trial, the study intervention must always be suspect. To help assess, the following guidelines are used.

- **Related** – *The AE is known to occur with the study intervention, there is a reasonable possibility that the study intervention caused the AE, or there is a temporal relationship between the study intervention and event. Reasonable possibility means that there is evidence to suggest a causal relationship between the study intervention and the AE.*
- **Not Related** – *There is not a reasonable possibility that the administration of the study intervention caused the event, there is no temporal relationship between the study intervention and event onset, or an alternate etiology has been established.*

7.2.3 Expectedness

Expected adverse reactions are AEs that are common and known to occur for the study intervention being studied and should be collected in a standard, systematic format using a grading scale based on functional assessment or magnitude of reaction. Describe the method of determining the expectedness of an AE. Expectedness refers to the awareness of AEs previously observed, not on the basis of what might be anticipated from the properties of the study intervention.

7.3 Time Period and Frequency for Event Assessment and Follow-Up

The occurrence of an AE or SAE may come to the attention of study personnel during study visits and interviews of a study participant presenting for medical care, or upon review by a study monitor. All AEs including local and systemic reactions not meeting the criteria for SAEs will be captured on the appropriate RF. Information to be collected includes event description, time of onset, clinician's assessment of severity, relationship to study intervention (assessed only by those with the training and authority to make a diagnosis), and time of resolution/stabilization of the event. All AEs occurring while on study must be documented appropriately regardless of relationship. All AEs will be followed to adequate resolution.

Any medical condition that is present at the time that the participant is screened will be considered as baseline and not reported as an AE. However, if the study participant's condition deteriorates at any time during the study, it will be recorded as an AE. UPs will be recorded in the data collection system throughout the study.

Changes in the severity of an AE will be documented to allow an assessment of the duration of the event at each level of severity to be performed. AEs characterized as intermittent require documentation of onset and duration of each episode.

CONFIDENTIAL

The PI will record all reportable events with start dates occurring any time after informed consent is obtained until 7 (for non-serious AEs) or 30 days (for SAEs) after the last day of study participation. At each study visit, the investigator will inquire about the occurrence of AE/SAEs since the last visit. Events will be followed for outcome information until resolution or stabilization.

All unresolved adverse events should be followed by the investigator until the events are resolved, the subject is lost to follow-up, or the adverse event is otherwise explained. At the last scheduled visit, the investigator should instruct each subject to report any subsequent event(s) that the subject, or the subject's personal physician, believes might reasonably be related to participation in this study. The investigator should notify the study sponsor of any death or adverse event occurring at any time after a subject has discontinued or terminated study participation that may reasonably be related to this study.

7.4 Reporting Procedures – Notifying the IRB

7.4.1 Adverse Event Reporting

At each contact with the subject, the investigator must seek information on adverse events by specific questioning and, as appropriate, by examination. Information on all adverse events should be recorded immediately in the source document. All clearly related signs, symptoms, and abnormal diagnostic procedures results should be recorded in the source document, though should be grouped under one diagnosis.

All adverse events occurring during the study period must be recorded. The clinical course of each event should be followed until resolution, stabilization, or until it has been determined that the study treatment or participation is not the cause. Serious adverse events that are still ongoing at the end of the study period must be followed up to determine the final outcome. Any serious adverse event that occurs after the study period and is considered to be possibly related to study participation should be recorded and reported immediately.

7.4.2 Serious Adverse Event Reporting

If the report is supplied as a narrative, the minimum necessary information to be provided at the time of the initial report includes:

- Study identifier
- Study Center
- Subject number
- A description of the event
- Date of onset
- Current status
- Whether study treatment was discontinued
- The reason why the event is classified as serious
- Investigator assessment of the association between the event and study treatment

7.4.3 Unanticipated Problem Reporting

Incidents or events that meet the OHRP criteria for UPs require the creation and completion of an UP report form. It is the site investigator's responsibility to report UPs to their IRB and to the DCC/study sponsor. The UP report will include the following information:

- Protocol identifying information: protocol title and number, PI's name, and the IRB project number;
- A detailed description of the event, incident, experience, or outcome;
- An explanation of the basis for determining that the event, incident, experience, or outcome represents an UP;

CONFIDENTIAL

- A description of any changes to the protocol or other corrective actions that have been taken or are proposed in response to the UP.

To satisfy the requirement for prompt reporting, UPs will be reported using the following timeline:

- UPs that are SAEs will be reported to the IRB and to the DCC/study sponsor within <insert timeline in accordance with policy> of the investigator becoming aware of the event.
- Any other UP will be reported to the IRB and to the DCC/study sponsor within <insert timeline in accordance with policy> of the investigator becoming aware of the problem.
- All UPs should be reported to appropriate institutional officials (as required by an institution's written reporting procedures), the supporting agency head (or designee), and OHRP within<insert timeline in accordance with policy> of the IR's receipt of the report of the problem from the investigator.

7.4.4 Reporting of Pregnancy

N/A

7.5 Reporting Procedures – Notifying the Study Sponsor

N/A

7.6 Reporting Procedures – Participating Investigators

N/A

8 Study Oversight

There will be no formal data and safety monitoring board for this protocol, as there is only minimal risk associated with participation in the current study. We will employ an internal Data Safety Monitoring Plan, managed by [name], and communicate with staff to ensure adequate risk assessment, adverse event reporting, compliance with protocol, and drop-out rates, with monthly review of safety data and appropriate reporting requirements to the NYU Langone Health IRB. Should unanticipated reportable events, defined as internal or external events (such as deaths, life-threatening experiences, injuries, breaches of confidentiality, or other problems), occur at any time during or after the research study, [name] will report them immediately to the NYU Grossman School of Medicine IRB. Any new information indicating a change to the risks or potential benefits of the research, any deviation from the protocol, and any possible serious or continued non-compliance will be reported to the NYU Langone Health IRB by [name] immediately.

CONFIDENTIAL

9 Statistical Considerations

9.1 Statistical and Analytical Plans

There will not be a formal SAP in this study, as it is a pilot with only 10 participants. Demographics will be compared between members of the intervention and control groups to assess the success of the randomization process. T-tests will be used to compare phthalate metabolite and bisphenol levels between the two groups and correlations of chemical levels will be run comparing mothers and infants in the control group.

9.2 Statistical Hypotheses

Aim 1: H1: We will successfully recruit participants from within an existing cohort study and collect biosamples from participants and their children in a single follow-up study visit.

Aim 2: Chemical levels will be higher among infants in the control group vs. the intervention group. There will be no difference in average chemical concentrations between the two groups of mothers. Among controls, different chemicals will be present in breast milk vs. infant urine.

9.3 Analysis Datasets

We will perform both ITT analysis as well as Per-Protocol Analysis, based on participants' self-reported compliance, which will be assessed periodically throughout the intervention.

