4.2 Exclusion Criteria

An individual who meets any of the following criteria will be excluded from participation in this study:

1. Not enrolled in NYU CHES study from the NYULH-Brooklyn campus
2. Under 37 weeks gestation or having had a preterm birth
3. Carrying multiples or having given birth to multiples
4. Not intending to breastfeed or not currently breastfeeding
5. Not comfortable communicating in English or Spanish
6. Not intending to obtain/obtaining pediatric care for infant at NYULH Sunset Park Family Health Center
7. Under 18 years of age

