4.7 Participant Withdrawal or Termination

4.7.1 Reasons for Withdrawal or Termination

Participants are free to withdraw from the study at any time upon request and with no consequence.

An investigator may terminate participation in the study if:

- Any clinical adverse event (AE), laboratory abnormality, or other medical condition or situation occurs such that continued participation in the study would not be in the best interest of the participant.
- The participant meets an exclusion criterion (either newly developed or not previously recognized) that precludes further study participation.

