4.7.2 Handling of Participant Withdrawals or Termination

If a participant withdraws between the time of consent and biospecimen collection, the participant will be replaced.

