9.4.6 Enrollment/Randomization/Masking Procedures

Participants will be assigned to either the intervention or control group on an alternating basis upon enrollment. Because of the nature of the intervention (cloth vs. conventional diapers), they will not be blinded. If a participant needs to be replaced, the replacement will be assigned to the same group as the participant who withdrew.

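### Once anyone leaves before sampling, the ITT analysis promised in section 9.3 can only be an analysis of completers as assigned, and the completion percentage has no stated denominator

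*Combined protocol and SAP*

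**What the plan says.** Section 9.3 names two analysis sets: "We will perform both ITT analysis as well as Per-Protocol Analysis". The second rests on compliance as participants report it themselves. The section does not say who belongs to the ITT set.

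Three other rules decide who can be in it:

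- Section 4.7.2: "If a participant withdraws between the time of consent and biospecimen collection, the participant will be replaced".
- Section 9.4.6: "If a participant needs to be replaced, the replacement will be assigned to the same group as the participant who withdrew".
- Section 6.3.6: "No procedures or evaluations will be done and no biospecimens will be collected if a participant withdraws or is terminated early".

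The outcomes of the between-arm comparison are concentrations (9.4.2) measured in specimens from a single visit, about two to three months in (6.1.1, 6.3.5). Section 4.6 expects usable data from every participant, and no method for missing outcomes is given.

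One of the grounds on which section 4.7.1 lets the investigator end participation is: "The participant meets an exclusion criterion (either newly developed or not previously recognized) that precludes further study participation". Section 4.2 lists as an exclusion criterion: "Not intending to breastfeed or not currently breastfeeding".

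For feasibility, section 3.2.1 sets the primary endpoint as all 10 participants having used their products for three months with breast milk and infant urine collected. Section 9.4.4 adds a completion percentage and average self-reported adherence by arm. It does not say whether a participant who was replaced counts in either.

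**The concern.** An ITT analysis keeps everyone in the arm to which they were assigned, whatever happens afterwards. Here the stated rules remove early leavers from the outcome data and fill their places in the same arm with people who stay. The label in 9.3 therefore promises something that the procedures prevent.

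Two things are at stake.

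- **The exploratory Aim 2 contrast.** The trial is open-label. Participants learn their arm at delivery, or at consent if they join postpartum. Loss after that point could differ by arm, and same-arm replacement would hide it.
- **The feasibility aim, which is primary.** Retention and adherence are the main things a pilot should report. If replaced participants drop out of the count, the retention figure shows only the people who were retained.

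A related gap concerns breastfeeding. If a mother stops after assignment and the investigator ends her participation under 4.7.1, section 6.3.6 also forfeits the infant's urine. That is the specimen used for the between-arm comparison of infants, and it does not depend on milk.

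**Working it through.** **1. The plan's own figure.** The sample size is 5 + 5 = 10, set by budget (9.4.5). No alpha, power, effect size or SD is given, so there is no sample-size formula to reproduce. No loss rate is given either.

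**2. Who can have an outcome?**

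| Participant | Sampled? | In the analysed set? |
|---|---|---|
| Stays, uses assigned products | Yes | Yes |
| Stays, stops using assigned products | Yes; 4.7.1 does not list this as a ground for termination | Yes; separated only in the per-protocol set |
| Withdraws before sampling | No (6.3.6) | No; replaced in the same arm (4.7.2, 9.4.6) |
| Terminated by the investigator | No (6.3.6) | No; replacement implied but not stated |

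The number of early leavers with outcome data is zero at any loss rate. The set is completers as assigned. It is wider than per-protocol and narrower than ITT.

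**3. Share of assigned pairs analysed.** With k participants replaced, the share is 10/(10 + k):

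- k = 1: 10/11 = 91%
- k = 2: 10/12 = 83%
- k = 3: 10/13 = 77%
- k = 4: 10/14 = 71%

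**4. How likely is it that the two sets coincide?** They coincide only if k = 0. For an assumed loss rate d, the chance that none of the first 10 leaves is (1 − d)^10, and the expected number assigned to reach 10 completers is 10/(1 − d):

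- d = 5%: 0.60; 10.5 assigned
- d = 10%: 0.35; 11.1 assigned
- d = 20%: 0.11; 12.5 assigned
- d = 30%: 0.03; 14.3 assigned

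**5. Feasibility figures.** If two participants leave and are replaced, completion reads 10/10 = 100% or 10/12 = 83%, depending on a denominator that 9.4.4 does not state. The endpoint in 3.2.1 can still be met, however many leave, as long as recruitment continues.

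**6. Possible bias in Aim 2 (illustration only).** On the log scale, let f be the share of an arm's assigned pairs who leave, and δ the mean difference in log concentration, leavers minus completers. The completers' control:intervention ratio divided by the as-assigned ratio is exp(f_I·δ_I − f_C·δ_C), with I for intervention and C for control. All inputs below are assumed:

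- Loss in the intervention arm only, leavers' levels twice those of completers (δ_I = ln 2): 2^0.2 = 1.15 at f = 0.2; 2^0.4 = 1.32 at f = 0.4.
- The same, with leavers half-way back on the log scale: 2^0.1 = 1.07 and 2^0.2 = 1.15.
- Leavers like completers, or equal f and δ in both arms: 1.00.
- Loss in the control arm only, leavers' levels twice those of completers: 1/1.15 = 0.87 and 1/1.32 = 0.76.

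For scale, with 5 per arm and an assumed log-SD of 0.5 to 1.0, the 95% interval multiplies and divides the ratio by exp(2.306 × SD × √(2/5)), which is about 2.1 to 4.3.

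**The case against.** The strongest reply is that little depends on this. Aim 2 is exploratory, the plan says it is underpowered, and 9.4.1 says the primary aim has no statistical endpoint. Any plausible bias is small beside the sampling error at 5 per arm. If all participants provide usable data, as 4.6 expects, the sets are identical. This stands as a reason not to rate the point higher. It does not make the label accurate, and it does not touch the completion percentage, which serves the primary aim.

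A reader might infer four stronger things that the documents do not support:

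- *Every terminated participant is replaced.* The sentences in 4.7.2 and 9.4.6 speak only of withdrawal. Replacement after termination is implied by the heading of 4.7.2 and by the all-10 endpoint in 3.2.1. Only the no-specimen rule expressly covers both.
- *The rules remove those in whom the intervention failed.* A mother who gives up the assigned products but stays enrolled is sampled and kept.
- *A mother who stops breastfeeding must leave.* Termination under 4.7.1 is discretionary and applies where the criterion precludes further participation. No section says that stopping breastfeeding does so.
- *The result will favor the intervention by 15% to 32%.* That needs a two-fold effect, leavers at control levels and loss in one arm only. None of these is documented. Section 4.3 describes both diaper types as in common use in this population, and cloth diapers come through a service. Withdrawals before delivery by prenatal enrollees cannot be a reaction to an arm they have not been told.

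**Conclusion.** The point holds and should be fixed. Under the stated rules the analysed set is completers as assigned: 10 of 10 + k assigned pairs, or 83% when two are replaced. It equals ITT only when nobody leaves. This follows from the text and needs no assumption about loss rates. If a terminated participant is not replaced, fewer than 10 pairs are analysed, and the set is still not ITT.

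The effect on the exploratory contrast is possible, but its size and sign are unknown. The illustrative factors run from 0.76 to 1.32, and every input to them is assumed. The effect on the feasibility report is more concrete: the same two losses can be reported as 100% or 83% completion. On breastfeeding, the documents leave an ambiguity and do not plan an exclusion.

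**What to change.** 1. **9.3, 4.7.2 and 9.4.6.** Define ITT as everyone assigned. Treat replacements as additional participants, keep the originals in the listing, and report missing outcomes by arm and reason.
2. **9.4.4.** Compute completion and adherence over all assigned participants, and show how many adherence reports each arm contributed.
3. **6.3.6.** Separate withdrawal of consent from early termination and from stopping the assigned products. From those who still consent, collect the available scheduled specimens and the questionnaire, and say how this applies to a participant terminated for a medical reason. Align the endpoint in 3.2.1, which now requires both milk and infant urine from everyone, with a possible missing milk sample.
4. **4.2, 4.7.1 and 6.3.6.** Reconcile these on whether stopping breastfeeding after assignment ends data collection. In 4.7.2, say whether a terminated participant is replaced.
5. **If item 3 is not adopted**, call the analysed set completers as assigned and not ITT.

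The cost is mostly wording in these sections, with a line in the consent form for item 3. A few pairs may lack milk, and a few sampled pairs beyond 10 are possible, which matters because the sample size was set by budget. Withdrawn consent will still leave some outcomes missing. The change is best made before any loss occurs, since an uncollected specimen cannot be recovered.
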